- 2. Patient reported outcome measures (PROMs), prompted via mobile-friendly questionnaires to study participants
- 3. Data from syncable devices provided to patients (Fitbit and Nokia Body digital weight scale for sleeve gastrectomy and gastric bypass patients; Fitbit and AliveCor, Kardia Mobile for catheter-based atrial fibrillation ablation patients)
- 4. Medication data from 2 major pharmacy chains (CVS or Walgreens)

Additionally, patients will be contacted by the RA via phone at 2 months to ascertain the health systems in which they sought care and the Hugo platform will be checked to ensure that data from those health systems is included (and patients will be asked to link those health systems or provide data, as appropriate). Multiple attempts will be made to contact patients if they are not contacted on the first attempt.

Bariatric surgery (either Sleeve Gastrectomy or Gastric Bypass) Patients Only

1. All patients enrolled in the study will then be asked to answer questions administered using the mobile health platform at baseline (pre-procedure), 1 week, 4 weeks, and 8 weeks post-procedure using validated symptom questionnaires from the National Institute of Health's PROMIS® (Patient-Reported Outcomes Measurement Information System), which we will adapt to a mobile format (See Appendix for original paper and mobile versions). These will ask about global health, pain, gastroesophageal reflux, nausea and vomiting, diarrhea,

constipation, and sleep. In addition, every Monday and Thursday for a total of 10 times immediately following their procedure, patients will be asked 2-4 questions on a visual analog scale related to pain and appetite. Please see Appendix for questionnaires as inputted into the mobile health platform as well as the original paper version.

- 2. We will attempt to sync the following data from syncable devices for study participants:
 - Fitbit (Ambulation, heart rate, and other activity), synced weekly
 - Digital weight scale, synced weekly
- 3. We will attempt to retrieve the following data from the electronic health record into Hugo for study participants:

Pre-procedural information

- Co-morbidities, prior surgeries, medications, and allergies
- Physician outpatient notes, including History & Physical

Intra- and post-procedural information during index hospitalization

- Duration of hospitalization
- Co-incident procedures at the time of sleeve gastrectomy or gastric bypass
- Re-operation or re-intervention
- Vital signs

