As each patient completes 8 weeks of follow-up, all patient data will be sent to the Mayo Clinic, where an analyst will clean and curate the data made available through the Hugo platform. The analyst will then send the cleaned data for the YNHH patients to the Yale investigator team. The RA will then confirm the primary diagnoses in the YNHH Electronic Medical Record (EMR) for physician visits, emergency department visits, and inpatient admissions during the 8-week period by examining and comparing to the research database to determine if any encounters or diagnoses are missing in the research database.

The data points that we will validate in the Hugo Research Database from the YNHH Epic EMR will be:

- Encounter date
- Encounter type
- Primary diagnosis for encounter

We will also note if any additional physician visits, emergency department visits, and inpatient admissions are seen in either system (in the case of additional points in Hugo, we will also determine if they are from another health system). If any diagnoses are missing in the Hugo Research Database, we will determine from which visit that they were missing.

In addition, we will examine YNHH EMR data to determine what new medications were prescribed at discharge, and then we will examine pharmacy data to determine which of these prescriptions were filled by the patient.

Finally, at the end of the pilot study (i.e. at 8 weeks post-procedure), study participants will be called by the RA and asked to complete a close-out questionnaire (see Appendix) to determine their satisfaction with the process of answering queries and provide the opportunity for them to offer comments and suggestions for

improvement. They will also be asked at what health systems they received care over the past 8 weeks (including hospitalization, emergency department visit, repeat procedure), to assess if all pertinent data was captured in Hugo.

Close-Out Questionnaire, whereby study participants are called by RA at 8 weeks on a HIPAA-protected secure phone line and asked:

- 1. How was your overall experience using this technology (open-ended)?
- 2. How long did it take you, on average, to answer the questions that you were sent weekly?
- 3. How was the experience of answering questions (open-ended)?
- 4. Did you have any of the following in the past 8 weeks:
 - a. emergency department visit
 - b. admission to a hospital
 - c. re-operation
 - d. major complication

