- 5. If yes to #4, what was the reason(s) for the emergency department visit, hospital admission, or re-operation?
- 6. In the past 60 days, at what health systems did you receive medical care? Do you have a portal with access for those health systems?
 - a. For patients who received care in a health system(s) connected to Hugo, we will ask the patient to obtain portal access and then link it to Hugo
 - b. For patients who received care in a health system(s) not connected to Hugo, we will ask the patient to obtain and upload their Continuity of Care Document (CCD) at the end of the study.

At the end of the study period, we will perform additional data abstraction by viewing the YNHH Electronic Medical Record, with the goal of augmenting our understanding of the specific procedures. If notes are available through Hugo at that time, then these notes will preferentially be viewed instead of those in the YNHH Electronic Medical Record. The specific elements that will be abstracted, with the anticipated sources, are as follows:

Pre-Operative History & Physical

-Indications for procedure (for example, for bariatric surgery the patient's BMI and presence of obesity-related co-morbidities; for atrial fibrillation, if the patient has failed pharmacologic therapies)

Operative Notes

- -Bariatric surgeon or cardiac electrophysiologist's technique
- -Additional procedures performed at time of index procedure
- -Medical devices used intra-procedure (if these are not available within the operative note, then we will determine if they can be found in a different place within the YNHH EMR)
- -Device failures or interventions (examples: staple line suturing, clips, or application of fibrin glue; additional devices required)

Discharge Summary

- -In-hospital adverse events
- -Diagnoses (including noting which diagnoses were present on admission and which were co-morbidities)
- -Discharge medications, where the prescribed medications will be compared to the medications that the patient received at discharge

5. Genetic Testing N/A ⊠

A. Describe

- i. the types of future research to be conducted using the materials, specifying if immortalization of cell lines, whole exome or genome sequencing, genome wide association studies, or animal studies are planned *Write here*
- ii. the plan for the collection of material or the conditions under which material will be received *Write here*

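### Outside YNHH, capture is checked only per health system, and close-out events carry no number, date or event-specific facility, so completeness there cannot be reliably judged

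*Protocol*

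**What the plan says.** All of this stands in the Protocol, Section I, item 4 (Research Plan).

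- **Phone contact at 2 months.** The research associate asks which health systems the patient used, and "the Hugo platform will be checked to ensure that data from those health systems is included". Where something is lacking, "patients will be asked to link those health systems or provide data, as appropriate".
- **Purpose at close-out.** The question on places of care is asked "to assess if all pertinent data was captured in Hugo".
- **Close-out item 4.** "Did you have any of the following in the past 8 weeks" is followed by four event types: emergency visit, hospital admission, re-operation and major complication.
- **Close-out item 5.** "If yes to #4, what was the reason(s) for the emergency department visit, hospital admission, or re-operation". Major complication is not named here.
- **Close-out item 6.** "In the past 60 days, at what health systems did you receive medical care", with follow-up on portal access and, for systems that Hugo does not connect to, upload of a continuity of care document.
- **YNHH care.** The date, type and primary diagnosis of each encounter are compared with the YNHH Epic record. Extra encounters in Hugo are traced to another health system where that is their source.

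The list of metrics (A to C) contains no capture rate for outside care.

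**The concern.** For YNHH care the protocol has an independent reference and compares encounter by encounter. For care elsewhere, the patient's own report is the only reference described that could reveal an event that Hugo missed. Tracing extra Hugo encounters to their source cannot do so, because it starts from what Hugo already holds.

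That report is collected without the fields that an event-level comparison needs, and the check described asks only whether a system is represented. Whether a patient-led platform picks up an emergency visit or admission away from the index hospital is central to its use in surveillance. A check that a missing event can pass is weak evidence on that question. A later analysis plan cannot supply counts, dates or places that were never asked for.

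**Working it through.** The protocol states no capture rate, target or sample-size calculation on this point, so there is no figure to reproduce. The check is a comparison of passages, followed by an illustration with assumed inputs.

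**Step 1. The two references side by side**

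| | Care at YNHH | Care elsewhere |
|---|---|---|
| Reference | Epic record | Patient's report by phone |
| Unit compared | Encounter | Health system |
| Date | Yes | Not asked beyond the recall window |
| Event type | Yes | Yes or no, four types |
| Number of events | Follows from the encounters | Not asked |
| Diagnosis or reason | Primary diagnosis | Reason(s), not for major complication |
| Place | Known | Listed per patient, not per event |

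The recall windows also differ slightly: item 4 covers 8 weeks (8 × 7 = 56 days) and item 6 covers 60 days, a difference of 4 days.

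**Step 2. Which missing outside events would be noticed?**

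1. *System not linked, or linked with no data.* The check fails and the patient is asked to link or provide data. The gap is noticed.
2. *System linked at enrollment and showing only pre-procedure data, one later event.* The check passes as worded. Items 4 to 6 would often allow a match by type, reason, system and window, but no such match is described for outside care.
3. *Two events of one type at one system, one of them in Hugo.* The check passes, and the single yes in item 4 agrees with the one encounter found. The second event can be missed.
4. *Several systems, all showing data.* Item 6 does not say which system goes with which event. The procedure itself was at YNHH, so a patient with any outside care will normally name at least two systems. The Epic comparison shows whether YNHH accounts for an event of that type. If it does, a further outside event of the same type is not excluded.

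**Step 3. Illustration of size (assumed inputs)**

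Let p be the probability that one post-procedure encounter at an outside system reaches Hugo, and k the number of such encounters there, captured independently. If the system counts as included once any of them appears, the per-system figure is 1 − (1 − p)^k, against a per-encounter figure of p.

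| p | k = 1 | k = 2 | k = 3 |
|---|---|---|---|
| 0.5 | 0.500 (gap 0) | 1 − 0.5² = 0.750 (gap 0.250) | 1 − 0.5³ = 0.875 (gap 0.375) |
| 0.7 | 0.700 (gap 0) | 1 − 0.3² = 0.910 (gap 0.210) | 1 − 0.3³ = 0.973 (gap 0.273) |
| 0.9 | 0.900 (gap 0) | 1 − 0.1² = 0.990 (gap 0.090) | 1 − 0.1³ = 0.999 (gap 0.099) |

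If older data from that system already satisfy the check, the per-system figure is 1 whatever p is, and the gap is 1 − p: 0.5, 0.3 and 0.1 for the three rows, even with a single encounter.

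**The case against.** The strongest reply is that the gap is narrow. Item 6 does ask "at what health systems did you receive medical care", and the text before the questionnaire ties that question to hospitalizations, emergency visits and repeat procedures. A reader might infer that no facility is recorded at all; that is not so, and only the link from event to place is missing. A reader might also infer that no reported event can be matched. One event at one outside system usually can be, from its type, reason, system and the 8-week window.

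The phone contact is also partly a step to complete the data, since unlinked systems are then linked. No passage says that the result will be reported as a percentage. How matches are counted could be left to an analysis plan. The close-out questionnaire sits in an appendix that is not shown, so further prompts cannot be ruled out. This is the Yale protocol, and the Mayo Clinic team obtains its own approval, so nothing here speaks to validation at that site. Finally, this is a 60-patient feasibility pilot without a clinical primary outcome.

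Most of this stands and limits the claim. It does not remove it. The close-out items are written out in the Research Plan and none asks for number, date or place of each event. The stated purpose is completeness of data, which is more than presence of a system. An analysis plan can define a match, but only on fields that were collected.

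**Conclusion.** The point holds as a limited design weakness that is cheap to mend. Outside YNHH, completeness is checked by presence of a health system, and the close-out answers do not reliably allow an event-level check when a linked system already holds older data or when a patient has several events or systems. The aim of judging whether all relevant data reached Hugo cannot be reliably met there.

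A reader might conclude that capture is overstated. The documents do not show that: they define no outside capture rate, and with one relevant encounter per system and no older data the two readings coincide. Overstatement is a risk of unknown size. The gaps of 0 to about 38 percentage points, and of 10 to 50 points with older data, rest on assumed p and k, on independent capture, and on the per-system result being read as a capture figure.

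Nor would a patient with one emergency visit at YNHH and one elsewhere simply be read as fully captured. The Epic comparison would identify the first as YNHH care and item 6 would name the other system. The missing visit goes unnoticed only if that other system is already represented in Hugo.

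**What to change.** For each yes in close-out item 4, record the number of events and, for each one, the facility and approximate date. Then check whether Hugo holds an encounter of that type at that facility within a stated window around the reported date (7 days, for example). Report events found over events reported, separately for YNHH and for other facilities. While the items are open, use one recall window for items 4 and 6 and let item 5 cover major complications.

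The cost is a small amendment to the questionnaire and a few more minutes on a call already planned, only for patients who report an event. Recalled dates are imprecise, which is why a window is needed, and events that the patient does not report remain outside the denominator. The capture figure may turn out less favourable.

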Because the mobile health platform (Hugo) obtains patient data through patient portals, all patients who connect will need a YNHH MyChart account. The RA will assist the patients in creating a MyChart account. On a desktop computer, the RA will log into her YNHH Epic Hyperspace account. She will look up the given patient and then enable the patient to obtain a MyChart account through the "Launch MyChart Signup" functionality. The patient will then confidentially create a MyChart account (the RA's YNHH Epic Hyperspace account is automatically locked) by entering his/her own username, password, and retyping the password. Once the patient has completed the MyChart sign-up process, then the RA will assist the patient in creating and activating an account for the mobile health platform, Hugo, on the patient's personal smartphone. Some patients may need to reset their MyChart password, and the RA will enable them to do so. Some patients may have forgotten their MyChart username, and the RA will be able to provide this information to them through the "Launch MyChart Signup" functionality. The RA will also assist the patient in connecting their mobile health platform account with other health systems where they have received care by showing the study participant how to enter their patient portal credentials, provided that these health systems are connected to the mobile application, as well as to pharmacy portals where they have received medications (if that includes CVS or Walgreens). Patients will also receive a syncable device relevant to their procedure (i.e. AliveCor Kardia Mobile for catheter ablation of atrial fibrillation or Nokia Body digital weight scale for bariatric surgery patients and Fitbit for all patients). At this time, patients will also complete their pre-operative/baseline questionnaires so that the RA is present to assist them. The RA will also ask patients to obtain and upload their continuity of care document (CCD) if they receive care in a health system that is not connected to Hugo, at both enrollment and again at 8 weeks; the RA will also ask patients to obtain credentials, if necessary, and connect portals to health systems where they receive care that are connected to Hugo but were unable to connect at enrollment. Patients will also receive a follow-up email from the RA that includes user guides for the devices they have received (Appendix).

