- All associated secondary diagnoses during incident hospitalization
- Transfer to intensive care unit
- Post-operative imaging tests obtained (e.g. CT scans)
- Physician notes, including Operative Report and Discharge Summary

Post-procedural encounters after hospital discharge for 8 weeks

- Number of encounters
- Encounter type (e.g. outpatient visit, inpatient visit, labs, imaging)
- Diagnoses associated with encounters
- Physician notes
- Lab tests and Imaging test results
- 4. We will test the feasibility of obtaining medication data from major pharmacy chains (Walgreens or CVS), including active prescription names, formulations and dosages, days' supply or # dispensed, frequency of fills, and prescriber.

Patients will receive automatic reminders to complete questionnaires daily for 2 days via email. Similarly, patients will receive automatic reminders to sync their digital scale and Fitbit weekly for 2 days after the planned sync date.

Catheter-based atrial fibrillation ablation patients only:

1. All patients enrolled in the study will then be asked to answer questions administered using the mobile health platform at baseline (pre-procedure), 1 week, 4 weeks, and 8 weeks post-

procedure using validated, symptom questionnaires from the National Institute of Health's PROMIS® (Patient-Reported Outcomes Measurement Information System) as well as the C-CAP1 and C-CAP 2 (Cardiff Cardiac Ablation PROMS 1 and 2)6, which we will adapt to a mobile-friendly format (See Appendix for original paper and mobile versions). These will relate to global health, dyspnea, and fatigue as well as symptoms related to atrial fibrillation and symptoms after ablation, including possible complications. In addition, every Monday and Thursday for a total of 10 times immediately following their procedure, patients will be asked 2-4 questions on a visual analog scale related to pain and palpitations. Please see Appendix for questionnaires as inputted into the mobile health platform as well as the original paper version.

- 2. We will attempt to sync the following data from syncable devices for study participants:
 - Fitbit (Ambulation, heart rate, and other activity), synced weekly
 - AliveCor (single lead electrocardiographic recording), synced weekly
- 3. We will attempt to retrieve the following data from the electronic health record into Hugo for study participants:

Pre-procedural information

- Co-morbidities, prior surgeries, medications, and allergies

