- Physician outpatient notes, including History & Physical

Intra- and post-procedural information during index hospitalization

- Duration of hospitalization
- Co-incident procedures at the time of atrial fibrillation ablation
- Re-intervention or other procedures (pericardiocentesis, cardioversion)
- Vital signs
- All associated secondary diagnoses during incident hospitalization
- Transfer to intensive care unit
- Post-operative imaging tests obtained (e.g. CT scans)
- Physician notes, including Operative Report and Discharge Summary

Post-procedural encounters after hospital discharge for 8 weeks

- Number of encounters
- Encounter type (e.g. outpatient visit, inpatient visit, labs, imaging)
- Diagnoses associated with encounters
- Physician notes
- Lab tests and Imaging test results
- 4. We will test the feasibility of obtaining medication data from major pharmacy chains (Walgreens or CVS), including active prescription names, formulations and dosages, days' supply or # dispensed, frequency of fills, and prescriber.

Patients will receive automatic reminders to complete questionnaires daily for 2 days via email. Similarly, patients will receive automatic reminders to sync their AliveCor and Fitbit weekly for 2 days after the planned sync date.

The metrics we plan to collect are as follows:

A. Enrollment-related

- Number of people asked for study participation and number enrolled
- Number of study participants who required assistance setting up Yale-New Haven Hospital or Mayo Clinic portals
- Number who had YNHH or Mayo portals who could not be enrolled (e.g. because they had forgotten password, no space on mobile device, technical glitch, etc)
- Time to set up new Hugo account and enroll patient in study
- Total enrollment time (from initiation of conversation with RA to completion of connecting health system portals)

B. PROM-related (for all PROMs)

- Rate of opening PROM emails
- Rate of PROM survey response
- Mean time to PROM survey response
- Proportion of items completed
- Proportion of people who completed PROM survey after initial email or after 1 reminder

C. Mobile Device-related

• Proportion of people who sync their devices (AliveCor, digital scale, and FitBit) at 1, 2, 3, 4, 5, 6, 7, 8 weeks

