(http://hugophr.com/security), its Privacy Notice (http://hugophr.com/security), and Terms of Service (http://hugophr.com/terms-of-service)

Participants will undergo the possible inconvenience of filling out electronic patient-reported outcome measure surveys, which should take approximately 60 minutes for the longer surveys (at baseline, 1 week, 4 weeks, and 8 weeks) and 15 minutes for the short surveys every Monday and Thursday a total of 10 times. Participants will also experience the possible inconvenience of wearing a Fitbit for extended periods of time as well as the possible inconvenience of utilizing and syncing the Kardia Mobile or Nokia Body Scale once a week. The estimated time required to sync the weight scale weekly for 8 weeks is 30 minutes, to sync the AliveCor weekly for 8 weeks is 30 minutes, and to sync the Fitbit weekly for 8 weeks is 15 minutes.

Although the Fitbit has been deemed a 'Low-Risk Device' by the FDA⁷ and is therefore not deemed medical grade⁸, there is the risk of inaccuracy in Heart Rate measurements. According to the Fitbit terms of service, found at www.fitbit.com/legal/terms-of-service, "The accuracy of the data collected and presented through the Fitbit Service is not intended to match that of medical devices or scientific measurement devices." The AliveCor Kardia Mobile device has been approved by the FDA as a 510k device since January 2015. In one published study of patients post-atrial fibrillation ablation that tested use of the AliveCor, only 2% of patients found it difficult to use⁹. However, as noted above, we will clearly state to the patients that this study should in no way impact their regular care plans.

11. Minimizing Risks: Describe the manner in which the above-mentioned risks will be minimized.

All patient data will be collected, handled, and stored according the most rigorous accepted standards. Staff involved in the study will be appropriately trained to maximize data security and technical systems will meet or exceed requirements imposed by HIPAA. Sensitive information will always be encrypted in transit (using secure file transfer protocols when data is obtained at Yale from the Mayo Clinic team that is cleaning and curating the data) and at rest. Paper documents at YNHH/CORE will be scanned into and saved onto a secure server. Once documents are scanned, the original documents will be shredded using a secure document destruction service.

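### Do the PROM metrics flatter remote completion by counting the staff-assisted baseline survey and averaging response time over responders only?

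*Protocol*

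**What the plan says.** Section I.4 (Research Plan) ends its procedures with a list of metrics to be collected. Block B is headed "B. PROM-related (for all PROMs" and has five items: the rate of opening the emails, the rate of survey response, "Mean time to PROM survey response", the proportion of items completed, and "Proportion of people who completed PROM survey after initial email or after 1 reminder". Block C, on device syncing, names weeks 1 to 8; block B names no time points.

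The long questionnaires are given "at baseline (pre-procedure), 1 week, 4 weeks, and 8 weeks post-procedure". The short ones are sent "every Monday and Thursday for a total of 10 times immediately following their procedure". Section I.10 (Risks) also counts baseline among the long surveys, giving "60 minutes for the longer surveys (at baseline, 1 week, 4 weeks, and 8 weeks". On the enrollment visit at Yale, Section I.4 says: "At this time, patients will also complete their pre-operative/baseline questionnaires so that the RA is present to assist them". Mayo's procedure is not described. On reminders: "Patients will receive automatic reminders to complete questionnaires daily for 2 days via email".

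Section I.1 makes completion of the patient-reported queries one of the items to be described under both aims. Section I.13 gives statistical considerations as not applicable, because this is a feasibility pilot with no specific clinical primary outcome.

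**The concern.** Three features of block B invite suspicion.

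- **Scope.** Taken literally, the heading includes baseline. A survey answered in clinic with staff beside the patient says little about whether people answer surveys on their own phones at home, which is what the pilot is meant to learn. One overall completion figure would be raised by it.
- **Mean time.** A survey that is never answered has no response time. With no rule for non-response, the mean can only be taken over those who answered, so it can fall when slow responders give up.
- **Reminders.** The reminder metric stops at one reminder, while the schedule most naturally means two.

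Completion is a named item of both aims, so a flattering figure could make the platform look more workable than it is.

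**Working it through.** **Inputs from the protocol.** There are 4 long and 10 short surveys per patient, 14 in all, and 60 patients (30 per site, 30 per procedure). Baseline is 1 of 14 surveys (7.1%; 60 of 840) and 1 of the 4 long ones (25%).

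The protocol states no response rate, so there is none to reproduce. Its participant-time total does confirm the survey count. Section VI.2 puts baseline inside the 4 set-up hours, and 4 + 3 × 1 + 10 × 0.25 + 8 × 0.5 + 8 × 0.25 = 15.5 hours, the stated maximum. That is 3 post-procedure long surveys and 10 short ones.

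**Assumptions.** Remote response p is 50, 60 or 70%. Baseline completion b is 100% (upper bound) or 90%.

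**Effect of baseline on the completion rate, if it were pooled.** The shift over all 14 surveys is (b − p)/14; over the four long surveys alone it is (b − p)/4. If only Yale's 30 baselines are assisted and Mayo's behave like remote surveys, each shift halves.

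| How reported | b | p = 50% | p = 60% | p = 70% |
|---|---|---|---|---|
| All 14 pooled | 100% | 3.6 points | 2.9 | 2.1 |
| All 14 pooled | 90% | 2.9 | 2.1 | 1.4 |
| All 14 pooled, Yale only assisted | 100% | 1.8 | 1.4 | 1.1 |
| All 14 pooled, Yale only assisted | 90% | 1.4 | 1.1 | 0.7 |
| Four long pooled | 100% | 12.5 | 10 | 7.5 |
| Four long pooled | 90% | 10 | 7.5 | 5 |
| By time point, post-procedure figures | any | 0 | 0 | 0 |

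Every non-zero row needs a pooling step that the protocol does not state. The block belongs to a list of metrics to be collected and is not a tabulation rule. Its heading can equally mean that each metric is obtained for each PROM; the ablation part of the same section uses that abbreviation in the names of the two Cardiff instruments. Two of the five metrics are defined by emails and reminders and do not naturally fit a survey completed in clinic.

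**Does the mean hide loss of responders?** Take 60 patients with reminders at 24 and 48 h, 20 each answering at 12, 36 and 60 h (illustrative times).

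- *All answer.* Mean (12 + 36 + 60)/3 = 36 h; response 60/60 = 100%; completed after the initial email or one reminder 40/60 = 67%.
- *The 20 slowest never answer.* Mean (12 + 36)/2 = 24 h; response 40/60 = 67%; initial email or one reminder 67% of surveys sent.
- *Half of the slowest never answer.* Mean (20 × 12 + 20 × 36 + 10 × 60)/50 = 31.2 h; response 50/60 = 83%; initial email or one reminder 67%.

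The mean does fall, but the response rate, listed directly above it, falls from 100% to 67% or 83%.

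**Is the second reminder lost?** Over all surveys sent, the response rate minus completion after the initial email or one reminder gives completion after the second: 100 − 67 = 33%, 67 − 67 = 0% and 83 − 67 = 17% in the three cases. In this illustration the cumulative proportion answered by 48 h is the reminder metric and that by 72 h is the response rate. The 24 h figure, 20/60 = 33%, follows if the reminder metric's two steps are shown separately. A separate cumulative curve would add little.

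**The case for a change.** The best case for the concern is that the protocol itself fixes the scope of these metrics, and that the scope fits its own procedures poorly. Email-opening and reminder metrics make little sense for a survey done at the enrollment visit. The payment section treats baseline as part of set-up, and the syncing metrics show that the authors name time points when they want them. If someone pooled the four long surveys, the overstatement could reach 12.5 points under the assumptions above. A mean without a rule for non-response can in practice only describe responders, and if the reminder metric were computed among responders it would rise to 40/40 = 100% when the slowest third drop out.

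Much of this is true as description. Yale's baseline is assisted, the heading does not exclude it, and a table that shows baseline apart and labels the mean as being among responders would be easier to read. But that is a preference about presentation. The poor fit of the email metrics with baseline argues against reading the heading as an instruction to pool. Denominators, tabulation by time point and the handling of unanswered surveys are commonly settled in a statistical analysis plan; one may exist and is not shown, so their absence here is no defect. The misleading reading of the mean requires ignoring the response rate beside it.

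**Conclusion.** The concern does not hold. The protocol does not say that baseline will be merged with later surveys, and collecting these metrics for every PROM is compatible with sound reporting. By time point, the effect on post-procedure completion is zero. If all surveys were pooled, it would be 0.7 to 3.6 points, assuming remote response of 50 to 70% and baseline completion of 90 to 100%, with either Yale's baselines alone or those at both sites assisted. Larger figures need the further unstated choice of pooling only the four long surveys. The response rate exposes any loss of responders that the mean would miss, and second-reminder completions can be recovered by subtraction over all surveys sent. The study is a descriptive pilot, and no threshold, test, sample size or primary outcome rests on these metrics.
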